5.5 N/A

5.6 N/A

5.7 N/A

6.0 Data and Specimen Storage for Future Research

6.1 N/A

6.2 N/A

6.3 N/A

7.0 Sharing of Results with Subjects

7.1 An individual participant's assessment results from questionnaires and interviews will be shared with that individual participant verbally at the end of each visit during which the assessment occurred (i.e., baseline, mid-treatment, post-treatment).

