5.0 Procedures Involved

This study will use feasibility randomized controlled efficacy trial design. This single-site trial will include up to 60 adults with self-reported fear of dogs, snakes, and/or spiders who will be randomly assigned via the REDCap Randomization Module using a 1:1 allocation ratio to receive 12 sessions of exposure therapy over the course of 3 months via standard telemental health (TMH; $n=15$) vs. Doxy.me VR ($n=15$), a telemedicine-based virtual reality clinic. Participants randomized to the Doxy.me group will be provided with Quest 2 VR headsets with the Doxy.me VR application pre-loaded to the device. This VR clinic is a standalone app currently available on Quest 2 headsets via

invite only. The app is designed for a therapist to meet with a client in a private, comfortable VR clinic office. To join each other in VR, the therapist selects a room code and provides that code to their client, who joins by entering that code into the app. While in the same VR room, the therapist and client can interact by speaking with each other in immersive VR. Therapists can also spawn a variety of small animals such as dogs, snakes, and spiders for use in treating specific phobias. Therapists can browse, select, maneuver, remove, and choose animations for the animals to exhibit once made visible to the client.

Therapy sessions will be audio recorded and 20% will be observed by the PI to assess treatment fidelity. Primary clinical outcomes (i.e., phobia severity as measured by the SMSF) will be assessed at baseline and 3-months post-baseline. Intervention targets will include presence—assessed weekly via patient-report— and working alliance—assessed at mid- and post-treatment via study therapist- and patient-report. Benchmarks for feasibility will include enrolling up to 60 patients during months 1-9 of the trial (i.e., 3/month), 70% patient retention at 3-month follow-up, 70% of weekly self-report collected, and $\geq 80\%$ treatment fidelity.

5.2 Please select the methods that will be employed in this study (select all that apply):

 Audio/Video Recording	 Psychophysiological Recording
 Behavioral Interventions	 Record Review - Educational
 Behavioral Observations and Experimentations	 Record Review - Employee

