All trial assessments are listed in Table 1 and were chosen considering several factors including (1) sound psychometric properties, (2) ease of administration, (3) past use in similar clinical trials, and (4) brevity. All questionnaires will be completed via REDCap

survey with study staff present via videoconference to answer any questions (see Measures in Local Site Documents and Figure 2. Study Schema and Schedule of Events).

[figure not shown]
Table 1. Study Assessments

[figure not shown]
Domain	Informant	Measure
Demographics	Patient	Patient Demographics Questionnaire
Anxiety Severity	Patient	General Anxiety Disorder-7 (GAD-7)(Johnson et al., 2019; Spitzer et al., 2006)
Depression Severity	Patient	Patient Health Questionnaire-9 (PHQ-9)(Kroenke et al., 2011, 2009)
Therapeutic Alliance	Patient Provider	Working Alliance Inventory- Short Revised (WAI-SR)(Hatcher & Gillasp, 2006) Working Alliance Inventory – Short Revised Therapist (WAI-SRT; (Hatcher & Gillasp, 2006)
Treatment Satisfaction	Patient	Client Satisfaction Questionnaire (CSQ-8)(Larsen et al., 1979)
Specific Phobia Severity	Patient	Severity Measure for Specific Phobia-Adult (SMSP-A; (Craske et al., 2013);
Specific Phobia Diagnosis	Patient	Diagnostic Assessment Research Tool (DART;(Schneider et al., 2022)
Presence	Patient	Single Item Presence Questionnaire (SIPQ; (S. Bouchard et al., 2005)
Cybersickness	Patient	Cybersickness in Virtual Reality Questionnaire (CSQ-VR; (Kourtesis et al., 2023)
Usability	Patient	System Usability Scale (Peres et al., 2013)

Treatment Fidelity

All treatment sessions will be recorded and 20% will be rated by the Supervisor (PI) using a Treatment Fidelity Checklist based on the treatment manual (see Treatment Data Collection Forms in Local Site Documents).

Figure 2. Study Schema and Schedule of Events

5.3 There are no procedures or interventions that are going to be conducted as part of this research project that would have been conducted even if the research was not occurring. We are conducting the procedures solely for research purposes.

5.4 There are no additional foreseeable risks to the above procedures in need of further mitigation beyond those ordinarily incurred in working with this population. Standard operational procedures of the USF Department of Psychiatry and Behavioral Neurosciences specify responsibilities for handling dangers to self and others, safety planning, and mandatory reporting responsibilities.

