8.0 Study Timelines

8.1 The study timeline with estimated visits and their accompanying durations can be viewed in Figure 2. Study Schema and Schedule of Events. Participants will participate in a ≤60-minute initial consent and baseline assessment visit (Visit 1). They will then participate in 12 ≤60-minute therapy sessions (Visits 2-13) and up to 6, ~30-minute homework assignments per week over 12 weeks. Participants will also participate in 20-minute mid- and post-treatment assessments, which will occur during Visits 7 and 13, respectively. In total, participants will spend approximately 38 hours over 13 study visits (i.e., Baseline + 12 Therapy Sessions) engaging in study procedures over the course of three months.

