16.0 Data Management and Confidentiality

16.1 We will assess feasibility of the proposed trial methodology using the following benchmarks: 30 participants will be enrolled in months 1-9 of trial, 70% of participants will be retained at three-month follow-up, 70% of weekly self-report assessments will be completed, and we will reach 80% or greater treatment fidelity.

The small sample size prevents any conclusions about efficacy; however, Analysis of Covariance will be used to conduct a preliminary assessment of between-group differences in clinical outcomes while co-varying for pre-treatment scores. We also will conduct a preliminary examination of associations between study targets including therapeutic alliance and presence.

16.2 D.

We will use the following security measures to protect data sources:

1. Data collected during the trial will be securely stored in a HIPAA compliant USF REDCap database, including informed consent documents, questionnaire data, and session notes.
2. Consent forms and de-identified data will be downloaded and stored in a secure HIPAA compliant Box folder.
3. All research data exported from REDCap will include ID numbers only.
4. Audio recordings will be stored in a secure HIPAA compliant USF Box folder.
5. Only IRB-approved and trained study personnel will have access to the REDCap project and box folder.
6. Computers, programs, and box folders containing data will be password-protected to prohibit unauthorized access.
7. The codes that link the name of the participant and the study ID will be kept confidential in REDCap along with other identifiers including first name, last name, full date of birth, address, email address, and cell phone number.
8. We have obtained a Certificate of Confidentiality from the National Institutes of Health so that we cannot be forced to disclose information that may identify participants, even by a court subpoena, in any federal, state, or local civil, criminal, administrative, legislative, or other proceedings.

16.3 We will use the following quality assurance measures for subject recruitment, enrollment, enrollment targets, and for the validity and integrity of the data:

1. study staff will complete and maintain up-to-date CITI and GCP training

2. study staff will be trained and supervised weekly by the PI
3. Standard Operating Procedures (SOPs) and study checklists will be used to train study staff and ensure fidelity to the study protocol

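### Section 7.1 does not except the patient-rated alliance form from verbal feedback at mid-treatment, so the post-treatment alliance rating may be reactive

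*Protocol*

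**What the plan says.** Protocol section 7.1 is a single sentence. Its subject is general: "An individual participant's assessment results from questionnaires and interviews". These results "will be shared with that individual participant verbally at the end of each visit during which the assessment occurred", and the visits are listed as "i.e., baseline, mid-treatment, post-treatment". No measure is excepted. The sentence does not say who gives the feedback or in what detail.

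Table 1 in section 5.0 lists the "Working Alliance Inventory- Short Revised (WAI-SR") as a patient-completed questionnaire, with a parallel therapist form. Section 5.0 names working alliance as an intervention target, "assessed at mid- and post-treatment via study therapist- and patient-report". Section 8.1 places the "20-minute mid- and post-treatment assessments, which will occur during Visits 7 and 13, respectively". Section 16.1 plans an exploratory look at "associations between study targets including therapeutic alliance and presence".

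**The concern.** A patient's rating of the working relationship with a therapist depends on the patient feeling free to answer candidly. If the result is discussed at the end of a session with that therapist, midway through treatment, two things can happen. The patient may answer differently the next time, expecting the rating to be discussed again. The discussion may also act on the alliance itself, although section 4.1 does not list it as part of either treatment.

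If the therapist hears the score, the therapist's own alliance rating may no longer be an independent report. At stake is the interpretation of one named intervention target and of the exploratory analysis that uses it. Ratings already recorded cannot be repaired at the analysis stage.

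**Working it through.** The protocol gives no figure that bears on this point, so the check is a cross-reading with simple visit arithmetic.

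1. **Is the alliance form covered by 7.1?** Section 7.1 covers questionnaires without exception, and Table 1 lists the WAI-SR as a patient questionnaire. Section 5.0 has it collected at mid- and post-treatment, both of which 7.1 lists. Read literally, the WAI-SR is covered, although 7.1 does not name it.

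2. **Where does the first disclosure fall?** Visit 1 is baseline and Visits 2–13 are the 12 therapy sessions (sections 4.1 and 8.1). Visit 7 is therefore therapy session 7 − 1 = 6, and 13 − 7 = 6 therapy visits remain.

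3. **Which alliance ratings can be affected?** There are two patient ratings.
   - The Visit 7 rating comes before any feedback on alliance.
   - The Visit 13 rating comes after it. Feedback at the end of Visit 13 comes too late to affect that patient rating.
   - So 1 of 2 time points follows disclosure, for every participant assessed at Visit 7. Section 11.1 aims for 30 participants with post-treatment data, 15 per arm, so as written all 30 who also had the Visit 7 assessment would be exposed.

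4. **Can the therapist learn the score?** The protocol does not say, but several statements make it possible.
   - Feedback falls at the end of a visit that the study therapist runs.
   - Under Treatment in section 5.0, the therapist sends the weekly survey link at the end of each session.
   - Section 16.2 puts questionnaire data and session notes in one REDCap database. Access is limited to approved, trained personnel, and no restriction by role is stated.
   - On the other side, section 5.0 says only that study staff are present while questionnaires are completed.
   - No order is given between the therapist's own rating and the feedback, so at either visit the therapist could rate after hearing the patient's result.

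5. **Which analyses depend on these ratings?**
   - The post-treatment alliance level.
   - The mid-to-post change, which compares a rating before disclosure with one after it.
   - The alliance–presence association in section 16.1.

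6. **Which results do not depend on them?** The benchmarks in section 16.1 are enrolment, retention, completion of weekly self-report and treatment fidelity. None uses an alliance score. Phobia severity, the primary clinical outcome, is stated in section 5.0 for baseline and 3 months only, so the text gives no mid-treatment severity score to feed back.

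The size of any shift cannot be computed. The protocol gives no standard deviation, alliance distribution or feedback effect.

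**The case against.** The case for leaving 7.1 alone is reasonable. Prompt return of results is a deliberate, participant-friendly choice. Participants hear a summary of answers they gave themselves. The trial is stated not to be powered for hypothesis testing, and the analysis concerned is preliminary. All of this limits the weight of the point. It does not remove it, because a written rule, not a missing detail, creates the exposure, and equal application in both arms does not protect an alliance level or a within-sample association.

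A reader might infer more than the protocol supports:

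- **Carry-over as a fact, across all post-treatment scores.** The text supports a possibility, and only for alliance among the measures whose timing can be read. The schedule figure is not available, so mid-treatment use of other measures can be neither confirmed nor excluded.
- **The therapist does learn the score.** This is plausible but not stated.
- **Participants already shade the Visit 7 rating because they expect disclosure.** What they are told beforehand cannot be seen in the available text.
- **Ratings are pushed upward toward a ceiling, shrinking any arm difference.** Nothing in the protocol gives a direction.
- **Telling participants their baseline severity score biases the primary clinical outcome.** The rule is the same in both arms, and the planned analysis of covariance compares arms with adjustment for pre-treatment scores. Between-arm bias would need reactivity that differs by arm, and nothing in the protocol shows that.

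**Conclusion.** The point holds as a limited one. As written, section 7.1 exposes the only alliance rating after mid-treatment to possible reactivity or reduced candour, and leaves open whether the therapist sees the patient's score. It applies to one of two alliance time points, for everyone assessed at Visit 7, by an amount that cannot be estimated from the protocol.

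This rests on two assumptions: that 7.1 is applied literally to the WAI-SR, and that no safeguard exists in site documents outside the protocol. The importance is modest, since it concerns an intervention target and an exploratory association in a feasibility trial. It is worth correcting because the change costs little and the same procedure could be carried into the efficacy trial that this study is meant to prepare.

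**What to change.** Amend section 7.1 so that the patient-rated alliance result is not shared until both the patient's and the therapist's post-treatment alliance ratings are complete, or the participant has withdrawn. Restrict the study therapist's REDCap access to WAI-SR scores until then, and tell participants so before they rate. Leave the sharing of all other results as written. Deferring nearly all results to the end of treatment would go further than the problem requires.

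The cost is a short wording change in 7.1 and in what participants are told, plus a user-rights setting in REDCap. The downside is that participants wait until the end of treatment for that one score.

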8.0 Study Timelines

8.1 The study timeline with estimated visits and their accompanying durations can be viewed in Figure 2. Study Schema and Schedule of Events. Participants will participate in a ≤60-minute initial consent and baseline assessment visit (Visit 1). They will then participate in 12 ≤60-minute therapy sessions (Visits 2-13) and up to 6, ~30-minute homework assignments per week over 12 weeks. Participants will also participate in 20-minute mid- and post-treatment assessments, which will occur during Visits 7 and 13, respectively. In total, participants will spend approximately 38 hours over 13 study visits (i.e., Baseline + 12 Therapy Sessions) engaging in study procedures over the course of three months.

9.0 Inclusion and Exclusion Criteria

9.1 In order to be eligible to participate in this study, an individual must meet all of the following criteria:

1. Is an adult ≥ 18 years old
2. Has a self-reported fear of dogs, snakes, and/or spiders
3. Indicates *Subthreshold* or *Present* Specific Phobia symptoms as determined by the study therapist via administration of the Diagnostic Assessment Research Tool (DART) Specific Phobia Module
4. Has access to the internet AND a computer OR smartphone with video conferencing capabilities
5. Will reside in the state of Florida for the duration of the study

9.2 An individual who meets any of the following criteria will be excluded from participation in this study:

1. Is participating in ongoing mental health therapy from a non-study therapist
2. Has had changes to psychotropic medication use within six weeks preceding enrollment in the trial
3. Reports active suicidal and/or homicidal intent or plan as determined by the study therapist via administration of the Diagnostic Assessment Research Tool (DART) Risk Assessment Module

4. Reports active auditory, visual, and/or tactile hallucinations via the Diagnostic Assessment Research Tool (DART) Psychosis Module screening question
5. Reports having a diagnosis of photosensitive epilepsy by a medical doctor or a history of experiencing seizures that they believe were caused by photosensitivity

9.3 An individual who meets any of the following criteria will become ineligible to continue on the study after enrollment:

1. Begins participating in ongoing mental health therapy from a non-study therapist
2. Has changes to psychotropic medication use
3. Does not indicate *Subthreshold* or *Present* Specific Phobia symptoms as determined by the study therapist via administration of the Diagnostic Assessment Research Tool (DART) Specific Phobia Module
4. Reports active suicidal and/or homicidal intent or plan as determined by the study therapist via administration of the Diagnostic Assessment Research Tool (DART) Risk Assessment Module
5. Moves out of the State of Florida during the study period

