The consent and baseline assessment visit will be conducted via video-conferencing platform and will not be audio or video recorded. During this visit study staff will (1) confirm the potential participant's responses on the Online Pre-Screening Questionnaire, (2) provide detailed information about the study and explain the informed consent document, (3) assist participants in completing baseline questionnaires via REDCap survey, (4) administer the Specific Phobia and Risk Assessment modules of the Diagnostic Assessment Research Tool (DART; See Measures document for specific items), and (5) make a final determination on the participant's eligibility. Eligible participants will then be randomized using the REDCap Randomization Module and scheduled for their first treatment visit (see Measures in Local Site Documents and Figure 2. Study Schema and Schedule of Events).

Treatment

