9.4 N/A

10.0 Vulnerable Populations

10.1 N/A

11.0 Local Number of Subjects

11.1 We aim to complete treatment with and obtain post-treatment assessment data from a total of 30 participants (15 in TMH and 15 in VR group). We will enroll up to 60 participants in the trial as needed to account for screen fails, withdrawals, and drops.

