12.3 N/A

13.0 Withdrawal of Subjects

13.1 Anticipated circumstances under which participants will be withdrawn from the research without their consent include the event that they:

1. Begin participating in ongoing mental health therapy from a non-study therapist
2. Have changes to psychotropic medication use
3. Begin to report active suicidal and/or homicidal intent or plan
4. Begin to report active auditory, visual, and/or tactile hallucinations
5. Begin to report the occurrence of photosensitive epilepsy or seizures
6. Moves out of the State of Florida during the study period

13.2 If subjects completely withdraw from the research, study staff will attempt to provide them with a referral to a therapist in their area. If subjects partially withdraw from the research, study staff will attempt to administer mid- and post-treatment assessments. Subjects will be given the option to completely withdraw from the study including withdrawing previously collected data.

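### Section 9.3 item 3 sets no time point and, read literally, ends participation when phobia symptoms remit; it needs reconciling with 13.1, 7.1 and the baseline visit

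*Protocol*

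**What the plan says.** Section 9.3 opens with "An individual who meets any of the following criteria will become ineligible to continue on the study after enrollment". Its third item reads "Does not indicate *Subthreshold* or *Present* Specific Phobia symptoms", as judged by the study therapist with the DART Specific Phobia module. It mirrors inclusion criterion 3 in section 9.1. It gives no visit, no time limit and no exception for response to treatment.

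Four other places bear on it:

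- **Section 5.0, Consent and Baseline Assessment.** Staff "administer the Specific Phobia and Risk Assessment modules of the Diagnostic Assessment Research Tool" and then decide eligibility. After that, "Eligible participants will then be randomized using the REDCap Randomization Module". No other DART phobia assessment is described in the text.
- **Section 7.1.** For each participant, "assessment results from questionnaires and interviews will be shared with that individual participant verbally at the end of each visit" at which they were obtained, and baseline, mid-treatment and post-treatment are given as those visits. It does not say which interviews are repeated.
- **Section 13.1.** The list begins "Anticipated circumstances under which participants will be withdrawn from the research without their consent include the event that they" and has six entries. Loss of phobia symptoms is not among them. Hallucinations and photosensitive epilepsy or seizures are, although 9.3 lacks both.
- **Section 11.1.** "We will enroll up to 60 participants in the trial as needed to account for screen fails, withdrawals, and drops". Screen failures therefore count among the enrolled.

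Section 16.1 sets the 70% retention benchmark at three months and plans a preliminary ANCOVA adjusted for the pre-treatment score. Section 13.2 says mid- and post-treatment assessments will be attempted after a partial withdrawal. Nothing says whether a 9.3 exit is partial or complete, or how it counts toward retention.

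**The concern.** Most items in 9.3 are things that happen to someone already on study: starting outside therapy, changing medication, leaving the state. Set among them, item 3 reads as an on-study event too, and the event it describes is the intended benefit. Criterion 3 in 9.1 already keeps symptom-free people out at baseline, so an item meant only for baseline would be redundant. Because 9.1 also admits people at the Subthreshold level, some participants start one category away from meeting the item.

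If the item is applied during treatment and follow-up stops, exit depends on the outcome. It would also be more frequent in whichever arm works better. Two results are exposed: the preliminary arm comparison, and the retention benchmark, which is part of the primary feasibility objective. Separately, staff working from 9.3 and staff working from 13.1 could handle the same participant differently.

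**Working it through.** The protocol gives no power calculation, effect size or SD, so there is no stated figure to reproduce. The 70% is a target. The check is a comparison of passages, then two calculations of what would follow if the item were applied after randomisation.

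**Passages side by side**

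| Question | Points to baseline only | Points to on-study use |
|---|---|---|
| When is the DART phobia module given? | 5.0 describes it once, before randomisation | 7.1 mentions interviews at mid- and post-treatment; the DART is the only diagnostic interview in Table 1, which gives it no time point |
| What does enrolled mean? | 11.1 includes screen failures, so enrolment can precede the DART result | 5.0 describes the up to 60 as people who will be randomly assigned |
| Is the item needed at baseline? | 9.3 item 4 also repeats a baseline criterion | 9.1 item 3 already covers it |
| Is the item a withdrawal reason? | 13.1 omits it | 9.3 includes it |

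The schedule of events (Figure 2) is not available here, so neither reading can be confirmed from it.

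**Retention**

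Inputs: the 70% benchmark and 30 participants (16.1), so the threshold is 0.70 × 30 = 21. Assumptions: a share *q* is removed for remission and counted as not retained; other dropout *d* is independent of this.

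- Expected retention = (1 − *q*)(1 − *d*).
- Other dropout compatible with 70% = 1 − 0.70/(1 − *q*).
- Chance of meeting the benchmark = P(X ≥ 21), with X binomial, n = 30 and p = (1 − *q*)(1 − *d*). Here *d* = 0.15.

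| *q* | Other dropout compatible with 70% | p at *d* = 0.15 | P(at least 21 of 30) |
|---|---|---|---|
| 0 | 30% | 0.850 | 0.99 |
| 0.10 | 22.2% | 0.765 | 0.85 |
| 0.20 | 12.5% | 0.680 | 0.49 |
| 0.30 | 0% | 0.595 | 0.16 |

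**Arm comparison**

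Assumed model in SD units, 400,000 simulated per arm: correlation of baseline with later scores 0.5; correlation of mid- with post-treatment score 0.6; TMH improves by 1 SD, half of it by mid-treatment; VR improves by a further 0.50 SD at post-treatment, half of it by mid-treatment. Anyone scoring below a cut-off of −2, −1.5 or −1 is removed and their post-treatment score is lost. The ANCOVA of post-treatment score on arm and baseline is then fitted to those who remain.

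| Removal acts on | Cut-off | Removed, TMH / VR | ANCOVA difference (true 0.50) |
|---|---|---|---|
| Mid-treatment score | −2 | 7% / 11% | 0.47 |
| Mid-treatment score | −1.5 | 16% / 23% | 0.46 |
| Mid-treatment score | −1 | 31% / 40% | 0.45 |
| Outcome score itself | −2 | 16% / 31% | 0.32 |
| Outcome score itself | −1.5 | 31% / 50% | 0.25 |
| Outcome score itself | −1 | 50% / 69% | 0.19 |

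Over true differences of 0.3, 0.5 and 0.8 SD, mid-treatment removal keeps 0.89 to 0.96 of the difference. Removal on the outcome score keeps 0.36 to 0.65. With a true difference of zero, the fitted difference stays at zero in every case.

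**The case against.** A reader might infer that the protocol will remove responders, cut the treatment difference by half or more and record success as dropout. The documents do not support that as a certainty.

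- The only described DART phobia assessment precedes randomisation, and 11.1 counts screen failures as enrolled. A person who consents and then fails the DART fits the wording of 9.3 without any randomised participant being affected.
- The reference to interviews in 7.1 is collective. It does not establish that the DART is repeated.
- The 13.1 list is introduced as what anticipated circumstances include, so it need not be exhaustive. Its silence on remission suggests, if anything, that remitters are not withdrawn.
- The large attenuation needs removal on the outcome score itself. Section 8.1 places the post-treatment assessment at Visit 13, the last visit. A DART given then would leave nothing further to continue, and no text says the severity score would be discarded.
- No rule counts a 9.3 exit as lost, and 13.2 provides for assessment attempts after partial withdrawal.
- Section 2.2 says the trial is not powered for hypothesis testing, and 16.1 disclaims conclusions about efficacy.

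All of this stands and limits the claim to a conditional one. It does not remove the defect: the sentence as written has no time point, the sections differ, and the unpowered design does not protect the retention benchmark.

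**Conclusion.** The point holds as a wording defect with conditional consequences. Item 3 of 9.3, read literally, ends participation on remission. It does not fit with 13.1 or with the single described DART phobia assessment, and 7.1 leaves a repeat open.

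If it were applied at mid-treatment with outcome data lost, the attenuation would be modest (0.50 to about 0.45-0.47 SD). The range 0.19-0.32 SD is an extreme case. The effect on retention could matter more: at 15% other dropout, 20% removal counted as loss turns a near-certain pass (0.99) into an even chance (0.49). Every removal share, dropout rate, cut-off and correlation here is an assumption, because the protocol supplies none.

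There is no bias in the arm comparison if the DART is given only before randomisation, if post-treatment data are still collected and analysed, or if the true difference is zero. The retention figures apply only if remitters are counted as lost. Since the efficacy comparison is preliminary and the harm conditional, this should be corrected but is not a critical flaw.

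**What to change.** Reconcile 9.3, 13.1, 7.1 and the baseline eligibility step in 5.0, with the sponsor stating when item 3 applies and whether the DART phobia module is repeated after baseline. Align the 9.3 and 13.1 lists, including the hallucination and seizure entries. Which continuation rule is right is for the sponsor to decide.

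Whatever is decided about treatment, add that a randomised participant whose DART status improves:

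- stays in mid- and post-treatment assessment, subject to their own right to withdraw under 13.2;
- counts toward the 70% retention benchmark when assessed;
- stays in the ANCOVA.

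With no removal for remission, the benchmark again tolerates 30% other dropout, and the simulated ANCOVA recovers the assumed 0.50 SD. The cost is a few lines of text and no added visits.
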